#### **8.6 Exploratory Endpoints**

1. Biosamples (blood and, where available, tumor) obtained will be obtained before treatment and at serial time points during treatment. Flow cytometry is used to analyze T cell subsets (including naïve, effector, memory (effector memory and central memory), effector memory RA, exhausted, Th1, Treg and Tfh), co-expression of sets of multiple inhibitory receptors by relevant T cell subsets, transcription factor expression, and T comprehensive functional analysis (expression of cytokines, chemokines, cytotoxic molecules, and degranulation).
2. Additional markers will be studied: CD3, CD4, CD8, CD25, CD39, CD73, CD127, FOXP3, CD122, CD212 (IL-12R), HLA-DR, CD14, CD19, CD56, CD69, FAS-L, Granzyme B, IL-2, IL-4, IL-10, IL-12, Rantes, IFN- $\gamma$ , TGF- $\beta$ , GM-CSF, sIL-2R.
3. Tumor FDG uptake will be measured on PET/CT at baseline and at 1-2 weeks after initiation of nivolumab. Based on change in tumor FDG uptake after initiation of nivolumab, FDG "flare", will be score as absent/present. FDG "flare" will likely be defined by >20% increase in tumor FDG uptake. This definition may be modified for the observed distribution of changes in tumor FDG uptake on our study.

#### **8.7 Interim Analysis**

No interim analysis is planned.

#### **8.8 Plans for Data Analysis**

1. Baseline and demographic characteristics will be summarized by standard descriptive statistics (including mean and standard deviation for continuous variables such as age and frequency and percentage for categorical variables such as gender).
2. The overall CR rate and 95% exact confidence interval will be calculated. Following an intent to treat analysis, all patients who received at least 1 dose of nivolumab are included in the analysis of the primary endpoint. Based on an exact binomial test, the number of patients with CR will determine whether the null hypothesis will be rejected (see Sample Size/Power below).
3. The nivolumab induction CR rate and post-RT + continued nivolumab CR rate and 95% confidence intervals will also be calculated.
4. Time to best response and duration of best response will be calculated and summarized separately for CR, PR, SD and PD patients.
5. Progression free survival, overall survival and disease-free survival will be estimated by the Kaplan-Meier method. Disease free survival will be computed by landmark analysis for two distinct groups: 1) DFS from week 8, for patients who achieved induction CR and 2) DFS from week 16, for patients who achieved CR after RT + nivolumab.
6. All subjects entered into the study will have detailed information collected on adverse events for the overall study safety analysis. Toxicities will be graded and tabled separately by induction nivolumab, post-induction nivolumab or post-induction RT + continued nivolumab.

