#### **4.4 Duration of Study Participation**

The duration of the study is approximately 22-25 weeks, from the time of pre-trial assessment through the final end-of-study visit. The duration of the intervention phase of the study is approximately 20-23 weeks: 8-12 weeks for nivolumab monotherapy, 8-12 weeks for continued nivolumab monotherapy vs. RT plus nivolumab, with 3 weeks allowed for RT simulation and planning. An additional 8-12 weeks is appended for patients undergoing additional RT.

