### 6.3.3 End of Study Visit

At the end of study visit – the second response assessment, 8-12 weeks after the first response assessment – FDG-PET will be performed, the patient will be evaluated for toxicities, and a final blood draw will be taken for correlative biomarkers. Patient charts will be reviewed for progression, response, and overall survival.

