## **8 Statistical Design**

This is a single arm Phase II clinical trial for relapsed/refractory Hodgkin lymphoma patients receiving nivolumab followed by either: a) continued nivolumab monotherapy if patient achieves an induction complete response (CR) scored at week 8, or b) RT (4 Gy x 2 fractions) plus continued nivolumab for patients who achieve <CR after induction. In the RT group, a second response assessment is undertaken at week 16, to determine the number of patients who have achieved CR. In both groups, nivolumab is continued until disease progression, drug intolerance, or at the discretion of the treating medical oncologist. continued until disease progression, drug intolerance, or at the discretion of the treating medical oncologist.

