### **8.5 Secondary Endpoints**

1. The nivolumab induction CR rate is defined as the proportion of patients who achieve CR after nivolumab induction, at the week 8 evaluation.
2. The post-RT + continued nivolumab CR rate is defined as the proportion of patients who achieve CR after RT + continued nivolumab, at the week 16 evaluation (8-12 weeks post-RT). All patients who had <CR are eligible to receive RT. The denominator will include all eligible patients, regardless of whether 2 fractions of RT were administered.
3. Time to best response is defined from date of study entry to date of best response. For progressive disease patients, time to best response will be defined from study entry to date taken off study due to PD. It is assumed that most patients who are scored PD at 8-12 weeks, will continue nivolumab for another 8 weeks.
4. Duration of best response is defined from date of best response to date of disease progression, death due to any cause of last patient contact alive and progression-free.
5. Progression free survival is defined from date of study entry to date of disease progression, death due to any cause of last patient contact alive and progression-free.
6. Overall survival is defined from date of study entry to date of death due to any cause of last patient contact alive.

CONFIDENTIAL

7. Disease-free survival is defined from date of CR to date of disease progression, death due to any cause of last patient contact alive and disease-free. DFS is only computed for CR patients.
8. Toxicities will be graded and tabled separately by induction or post-RT.

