#### **Adverse Event Reporting Period**

The study period during which adverse events must be reported is normally defined as the period from the initiation of any study procedures to the end of the study treatment follow-up. For this study, the study treatment follow-up is defined as 30 days following the last administration of study treatment.

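### Toxicity is tabled by treatment phase with inconsistent columns, no time denominator and an unsettled adverse-event window, so unequal observation time can pass for, or hide, an RT effect

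*Combined protocol and SAP*

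**What the plan says.** All references are to the combined protocol and SAP.

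- **Columns.** Section 8.8 item 6: "Toxicities will be graded and tabled separately by induction nivolumab, post-induction nivolumab or post-induction RT + continued nivolumab". Section 8.5 item 8: "Toxicities will be graded and tabled separately by induction or post-RT". The second wording has no place for post-induction toxicity in patients who receive no RT. Neither item mentions patients at risk, person-time or a fixed window.
- **Bounded window.** Section 4.4 gives the intervention phase as "8-12 weeks for nivolumab monotherapy, 8-12 weeks for continued nivolumab monotherapy vs. RT plus nivolumab, with 3 weeks allowed for RT simulation and planning", and adds: "The duration of the study is approximately 22-25 weeks, from the time of pre-trial assessment through the final end-of-study visit". Section 6.3.3 makes the end-of-study visit "the second response assessment, 8-12 weeks after the first response assessment", with a toxicity evaluation at that visit. Section 3.1.3 places later follow-up off study.
- **Open-ended window.** The opening of section 8: "In both groups, nivolumab is continued until disease progression, drug intolerance, or at the discretion of the treating medical oncologist". The Adverse Event Reporting Period in section 9.1.1: "the study treatment follow-up is defined as 30 days following the last administration of study treatment". Section 6.5 collects serious events for 90 days after treatment ends.
- **Repeat RT.** Section 4.4: "An additional 8-12 weeks is appended for patients undergoing additional RT".
- **Attribution.** Sections 6.2.3 and 6.2.4 have toxicities graded and attributed to nivolumab and to radiation respectively.

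**The concern.** Safety is secondary objective 6, and the trial has one arm. A reader who wants to know whether RT adds toxicity to nivolumab will compare the RT + nivolumab column with another column of the same table. The post-induction nivolumab column follows the same window rule as the RT column. At the 10% induction CR rate expected in section 4.5, however, it would hold about 2.5 of 25 patients, all complete responders. Induction is therefore the only sizeable internal reference.

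That comparison is fair only if the two columns cover similar time per patient, or if the time is shown. Neither AE window gives equal time, and the plan does not show it. A difference between the columns could then come from length of observation alone, in either direction.

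**Working it through.** **The plan's own figures.** No figure is stated for toxicity. The only design calculation (section 8.9) concerns the CR rate. It reproduces: P(X ≥ 6 | 25, 0.10) = 0.0334 and P(X ≥ 6 | 25, 0.30) = 0.8065, against the stated 3% and 81%. This point does not touch it.

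**Inputs from the documents.** Induction 8–12 weeks; post-induction 8–12 weeks plus 3 for RT planning (4.4); AE tail of 30 days = 4.3 weeks (9.1.1); 6-month PFS on nivolumab of 76.9% (1.2); study duration 2 years (Study Summary).

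**Assumptions.** The AE hazard is constant and RT has no effect. For the open-ended window, time on drug follows PFS with an exponential shape.

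**Bounded window.** Under a constant hazard, expected events per patient are proportional to weeks observed.
- Shortest against longest: 8/12 = 0.67.
- Longest against shortest: (12 + 3)/8 = 1.88.
- With the 30-day tail: (15 + 4.3)/8 = 2.41.

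These ratios leave out the repeat-RT extension, which lengthens only the RT column.

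**Open-ended window.**
- Rate of leaving nivolumab: h = −ln(0.769)/26.09 = 0.01007 per week.
- Mean post-induction time on drug over T weeks: (1 − exp(−hT))/h. This is 22.9 weeks for T = 26, 40.5 for T = 52, and 60.0–61.5 for T = 92–96 (2 years less induction).
- If 10% have a given event in induction, the AE hazard is λ = −ln(0.9)/8 = 0.01317 per week for an 8-week induction, or −ln(0.9)/12 = 0.00878 for 12 weeks.
- Post-induction percentage with the event: λ/(λ + h) × (1 − exp(−(λ + h)T)).

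| Follow-up after induction | 12-week induction | 8-week induction | Ratio to 10% |
|---|---|---|---|
| 26 weeks | 18% | 26% | 1.8–2.6 |
| 52 weeks | 29% | 40% | 2.9–4.0 |
| to 2 years (92 or 96 weeks) | 38% | 51% | 3.8–5.1 |

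The table leaves out the 30-day tail. The last row supposes that every patient enrols at the start. With uniform accrual over 52–78 weeks inside the 2 years (assumed), mean post-induction time falls to about 40–50 weeks and the percentages to 28–45%.

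**Whether person-time rates alone would do.** Suppose, for illustration, that RT doubled the AE hazard for 4 weeks. The person-week rate ratio over a window of T weeks is about 1 + 4/T. That is 1.50 for T = 8, but 1.10 for T = 40.5 and 1.07 for T = 61.5. A whole-phase rate would dilute an acute RT effect; a short matched window would not.

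**The case against.** The strongest reply is that these tables are descriptive. No between-phase test is planned, and section 9.5 states that there are no stopping rules. Toxicities are attributed to nivolumab and to radiation separately, so RT safety does not rest on the column contrast alone. All of this stands and limits the point to interpretation.

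A reader might infer that the RT column will look several-fold more toxic. The documents do not support that as a given. Sections 4.4, 6.3.3 and 3.1.3 allow a bounded study, where the ratio can fall below 1. The larger ratios need the open-ended window and a constant hazard. They would shrink if AEs cluster early in nivolumab treatment, with staggered accrual, or if drug is stopped for reasons other than progression. The PFS figure also comes from all treated patients, whereas the RT column holds only those without an induction CR.

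A reader might also infer that the tables will be raw counts, or that the trial can say nothing about RT safety. The text says only that toxicities are graded and tabled, and item 1 of section 8.8 uses frequencies and percentages for categorical variables. The open-ended calculation above uses percentages of patients, so the distortion does not depend on raw counts. Separate attribution and the small post-induction nivolumab column both carry some information.

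The two-against-three column mismatch could be called editorial, since 8.8 item 6 supplies the missing column. The two items still need to agree.

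**Conclusion.** The point holds as a worthwhile, low-cost improvement. Three facts need no modelling: the two items list different columns, neither gives a denominator or common window, and the documents support two AE windows. The size is conditional. With a constant AE hazard and no RT effect, the RT column would show about 0.67 to 1.9 times the induction toxicity per patient on the bounded window (at most about 2.4 with the 30-day tail, repeat RT aside). On the open-ended window it would show about 1.8 to 5 times the percentage of patients with an event of 10% induction incidence, and less under staggered accrual or early clustering. What is at risk is the reading of RT safety. The primary result, its error rate and the conduct of the trial are unaffected.

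**What to change.** 1. Reconcile sections 4.4, 6.3.3 and 3.1.3 with the opening of section 8, section 9.1.1 and section 6.5, so that one AE window (and one for serious events) applies to the tables.
2. Use the three columns of 8.8 item 6 in 8.5 item 8. Start the RT column at the first RT fraction, and say which column takes the weeks between the first response assessment and that fraction.
3. Beside the number and percentage of patients with events, report patients at risk and person-weeks for each column.
4. Make the main RT-safety summary an equal-length comparison: grade 3 or higher toxicity in the first 8 weeks of nivolumab against the first 8 weeks from the first RT fraction, with 95% confidence intervals. Give whole-phase person-time rates as supportive, because they dilute an acute effect.

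The window settled in step 1 must cover 8 weeks from the first fraction. If the second assessment came 8 weeks after the first and RT planning took 3, a window closing there would leave only 8 − 3 = 5 weeks.

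The cost is wording in a few sections and some table columns. It should need only dates that a trial normally records: first and last dose, RT fractions and AE onset. Two limitations should be stated. Intervals will be wide with about 22 RT patients: 2 of 22 (9%) has an exact (Clopper-Pearson) 95% interval of about 1% to 29%. The second window also holds patients who have already tolerated induction, so equal length does not make the two windows fully comparable.

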#### **Exploratory Analyses**

1. Longitudinal changes in biomarkers will be assessed by plots over time and descriptive statistics (mean, median, standard deviation, range and coefficient of variation). Change in markers from baseline to week 8, will be compared between nivolumab induction responders (CR) and non-responders (<CR). Change in markers from week 8 to week 16, will be compared between post-radiotherapy responders (CR) and non-responders (<CR). Tumor FDG uptake on PET/CT, from baseline to 1 week after nivolumab will be compared. Student's t-test or non-parametric Wilcoxon rank sum test will be employed.

CONFIDENTIAL

2. Change in tumor FDG uptake from baseline to week 1, will be assessed by paired t-test or Wilcoxon signed rank test.
3. The association between binary FDG "flare" and progression-free & overall survival will be tested using log rank test. Cox regression will be used to assess the effect of continuously scaled FDG change. For all survival analyses, a landmark analysis will be performed. Here, PFS or OS are defined from a landmark, which is 1-2 weeks after initiation of nivolumab.
4. The association between binary FDG "flare" and response will be tested by Fisher's exact test.
5. The association between binary FDG "flare" and biomarker changes will be assessed by Wilcoxon rank sum test.

## 8.9 Sample Size/Power

With 25 patients, there is 81% power to detect a difference of 20% assuming a null hypothesis that the CR rate = 10% versus an alternative hypothesis that the CR rate = 30% using a one-sided exact test with a 5% significance level. We will reject the null hypothesis if 6 or more of 25 patients achieve a CR. The actual significance level for this exact test procedure is 3%.

## 9 Safety and Adverse Events

### 9.1 Definitions

#### 9.1.1 Adverse Event

##### Unanticipated Problems Involving Risk to Subjects or Others

Any incident, experience, or outcome that meets all of the following criteria:

- Unexpected in nature, severity, or frequency (i.e. not described in study-related documents such as the IRB-approved protocol or consent form, the investigators brochure, etc)
- Related or possibly related to participation in the research (i.e. possibly related means there is a reasonable possibility that the incident experience, or outcome may have been caused by the procedures involved in the research)
- Suggests that the research places subjects or others at greater risk of harm (including physical, psychological, economic, or social harm).

#### Adverse Event

An **adverse event** (AE) is any symptom, sign, illness or experience that develops or worsens in severity during the course of the study. Concurrent illnesses or injuries should be regarded as adverse events. Abnormal results of diagnostic procedures are considered to be adverse events if the abnormality:

- results in study withdrawal
- is associated with a serious adverse event
- is associated with clinical signs or symptoms
- leads to additional treatment or to further diagnostic tests
- is considered by the investigator to be of clinical significance

#### Serious Adverse Event

Adverse events are classified as serious or non-serious. A **serious adverse event** is any AE that is:

- fatal
- life-threatening
- requires or prolongs hospital stay
- results in persistent or significant disability or incapacity
- a congenital anomaly or birth defect
- an important medical event

Important medical events are those that may not be immediately life threatening, but are clearly of major clinical significance. They may jeopardize the subject, and may require intervention to prevent one of the

CONFIDENTIAL

other serious outcomes noted above. For example, drug overdose or abuse, a seizure that did not result in in-patient hospitalization, or intensive treatment of bronchospasm in an emergency department would typically be considered serious.

All adverse events that do not meet any of the criteria for serious should be regarded as ***non-serious adverse events***.

#### **Adverse Event Reporting Period**

The study period during which adverse events must be reported is normally defined as the period from the initiation of any study procedures to the end of the study treatment follow-up. For this study, the study treatment follow-up is defined as 30 days following the last administration of study treatment.

#### **Preexisting Condition**

A preexisting condition is one that is present at the start of the study. A preexisting condition should be recorded as an adverse event if the frequency, intensity, or the character of the condition worsens during the study period.

#### **General Physical Examination Findings**

At screening, any clinically significant abnormality should be recorded as a preexisting condition. At the end of the study, any new clinically significant findings/abnormalities that meet the definition of an adverse event must also be recorded and documented as an adverse event.

#### **Hospitalization, Prolonged Hospitalization or Surgery**

Any adverse event that results in hospitalization or prolonged hospitalization should be documented and reported as a serious adverse event unless specifically instructed otherwise in this protocol. Any condition responsible for surgery should be documented as an adverse event if the condition meets the criteria for an adverse event.

Neither the condition, hospitalization, prolonged hospitalization, nor surgery are reported as an adverse event in the following circumstances:

- Hospitalization or prolonged hospitalization for diagnostic or elective surgical procedures for a preexisting condition. Surgery should **not** be reported as an outcome of an adverse event if the purpose of the surgery was elective or diagnostic and the outcome was uneventful.
- Hospitalization or prolonged hospitalization required to allow efficacy measurement for the study.
- Hospitalization or prolonged hospitalization for therapy of the target disease of the study, unless it is a worsening or increase in frequency of hospital admissions as judged by the clinical investigator.

#### **9.2 Recording of Adverse Events**

At each contact with the subject, the investigator must seek information on adverse events by specific questioning and, as appropriate, by examination. Information on all adverse events should be recorded immediately in the source document, and also in the appropriate adverse event module of the case report form (CRF). All clearly related signs, symptoms, and abnormal diagnostic procedures results should be recorded in the source document, though should be grouped under one diagnosis.

All adverse events occurring during the study period must be recorded. The clinical course of each event should be followed until resolution, stabilization, or until it has been determined that the study treatment or participation is not the cause. Serious adverse events that are still ongoing at the end of the study period must be followed up to determine the final outcome. Any serious adverse event that occurs after the study period and is considered to be possibly related to the study treatment or study participation should be recorded and reported immediately.

#### **9.3 Relationship of AE to Study**

An adverse event is defined as any untoward medical occurrence in a patient or clinical investigation subject administered a pharmaceutical product and which does not necessarily have to have a causal

CONFIDENTIAL

relationship with this treatment. An adverse event can therefore be any unfavorable and unintended sign (including an abnormal laboratory finding, for example), symptom, or disease temporally associated with the use of a medicinal product or protocol-specified procedure, whether or not considered related to the medicinal product or protocol-specified procedure. Any worsening (i.e., any clinically significant adverse change in frequency and/or intensity) of a preexisting condition that is temporally associated with the use of the study product, is also an adverse event. The Principal Investigator or an appropriate designee will determine the relationship of the adverse event.

#### **9.4 Reporting of Adverse Events, Adverse Device Effects and Unanticipated Problems**

Investigators must conform to the adverse event reporting timelines, formats and requirements of the various entities to which they are responsible, but at a minimum those events that must be reported are those that are:

- related to study participation,
- unexpected, and
- serious or involve risks to subjects or others

If the report is supplied as a narrative, the minimum necessary information to be provided at the time of the initial report includes:

• Study identifier

• Study Center

• Subject number

• A description of the event

• Date of onset

	

• Current status

• Whether study treatment was discontinued

• The reason why the event is classified as serious

• Investigator assessment of the association between the event and study treatment

---	--

